- **b.** Potential benefits to society (e.g. increased understanding of disease process). The current study is designed to address the important issue of language rehabilitation after aphasia-inducing stroke. Speech-language therapy is the treatment for aphasia, and relies heavily on behavioral therapies that implicitly engage systems of learning. Additional research is needed to demonstrate which types of therapies are efficacious for patients and how potential modifications to instruction method might impact therapy outcomes.

IX. MONITORING AND QUALITY ASSURANCE

a. Independent monitoring of source data

The PI or study staff will conduct ongoing review of data to ensure completeness, accuracy and compliance with protocols. Quarterly review will ensure that participant inclusion is in adherence with enrollment criteria, that records of subject enrollment are up to date, and that procedures and study visits are being completed as proposed. Review will be completed by the PI or study staff. In the event of an adverse event, the event will be immediately reviewed. Continuing reviews will be submitted in accordance with the IRB.

b. Safety monitoring (e.g., Data Safety Monitoring Board)

Protection of subject privacy: Forms containing personally identifying information (history forms and data collected during cognitive-linguistic assessments) will be kept in a locked filing cabinet at the MGH-IHP to which only the PI and approved study staff have access.

Deidentified assessment and treatment data will be transferred to a secure network maintained by Partners, which can only be accessed by the PI and approved study staff via electronic ID. These digital files will be coded with identification codes and will not contain personally identifiable information. A single subject file kept on the secure network, under additional password protection will be the only location that stores the link between study codes and subject identifying information. Deidentified standardized assessment scores collected on paper will be transferred from paper forms to digital forms and entered into RedCap, a HIPAA compliant, web-based software application hosted by Partners. Data will also be stored on Lab Archives and Partners Dropbox.

Video data will be kept on a secure network maintained by Partners and accessed only by approved researchers. Deidentified video clips will be kept for education purposes within MGB. If we do utilize videos, participant faces will be blurred/obscured as to remain de-identified. De-identified data are kept for possible future analyses, which will be submitted for approval. If we re-analyze data in the future, we will notify and submit an application for approval from the IRB.

Sending data to outside collaborators: Accuracy and response data from assessments and treatment tasks may be sent to research collaborators outside of Partners. We plan to contribute de-identified assessment results and spontaneous speech responses to the AphasiaBank by TalkBank (https://aphasia.talkbank.org/), which is a shared database of multimedia interactions for the study of communication in aphasia. Access to the data in AphasiaBank is password protected and restricted to members of the AphasiaBank consortium group. All data will be coded with study codes only and will not contain identifiers.

Receiving data from outside collaborators: No data will be received from outside of Partners.

d. Adverse event reporting guidelines: Since the risks associated with participation in this study are low, we do not anticipate serious adverse events. In the case of an adverse event, the event will immediately be assessed and the IRB office will be contacted. Participant confidentiality will be maintained unless otherwise directed and approved by the IRB.

X. REFERENCES

- 2. American Speech-Language-Hearing Association (n.d.). *Aphasia* (Practice Portal). Retrieved November 23, 2020 from www.asha.org/Practice-Portal/Clinical-Topics/Aphasia/.
- 3. Antonucci, S. M. (2009). Use of semantic feature analysis in group aphasia treatment. *Aphasiology*, 23(7-8), 854-866.
- 5. Azios, J. H., Archer, B., & Lee, J. B. (2020). Detecting behavioural change in conversation: procedures and preliminary data. *Aphasiology*, 1-23.

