1b. Determine whether patients with aphasia learn the strategy and consequently demonstrate a change in their language behavior in moments of naming difficulty. Hypothesis: We hypothesize that strategy training will lead PWA to correctly identify the strategy's components post-treatment. We also hypothesize that strategy training will lead PWA to produce more feature words (i.e., engage in circumlocution) during moments of naming difficulty. Specifically, we expect to find medium to large effects on the number of feature words PWA produce during naming attempts post-treatment.

Aim 2. Evaluate the effect of strategy training on patients' language production during connected speech. Approach: We will collect and transcribe connected speech samples, including spoken descriptions of pictures, weekly activities, and personal memories⁷³, pre- and post-treatment. Hypothesis: We hypothesize that strategy training will lead PWA to produce more object and feature words during connected speech. We expect medium to large effects on object words, feature words, and measures of communicative effectiveness⁶⁴.

III. SUBJECT SELECTION

a. Inclusion/exclusion criteria.

Eligible individuals will:

- Experienced a single left-hemisphere stroke,
- Have aphasia due to stroke,
- Be in the chronic stages of their aphasia, at least 6 months post onset of stroke,
- Be between the ages of 18 and 89 years of age, and
- Be a proficient English speaker,
- Have no history of neurodegenerative disease, severe motor speech disorder, significant mental illness, psychiatric disorder, drug/alcohol abuse, or neurological condition that could influence their cognitive, language, and memory systems.

Participants may have concomitant medical problems such as heart disease or diabetes; however, at the time of their participation they will be medically and neurologically stable and at least wheelchair ambulatory.

Participants with a history of minor head injury or short-term loss of consciousness are eligible to participate, however a brief history of these instances will be obtained in order to control for potential secondary impacts to learning and memory systems. Similarly, history of developmental learning disorders will be obtained, as this can affect learning and strategy development/compensatory systems, which are a focus of our research study.

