a. Methods of enrollment. We plan to enroll 20 individuals with aphasia in a single-subject design intervention study in which all participants receive the same intervention protocol.

b. Procedures for obtaining informed consent. Once interest in participating in the study is expressed, one of the co-investigators involved in this study will establish contact with potential participants over the phone or via email. The research project will be explained and interested persons will be invited to the research site to discuss the study. The purpose, procedures, possible benefits and risks of the study will be explained to all potential participants. Potential participants will also be instructed that they can withdraw from the experiment at any time.

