- (a) provide education on object naming,
- (b) work with the participant to develop strategies to quickly identify instances in which they are unable to name an object,
- (c)teach the participant to immediately begin generating feature words, i.e., circumlocuting, once they realize they are unable to name an object, and
- (d1) teach the participant the six types of feature words they can produce during circumlocution (i.e., the six SFA framework components, Figure 2 below). The clinician and the participant will work together to learn and memorize the six components. Once the participant is able to independently identify four of the six components across three sessions, *Strategy Education* will change as follows.

- The clinician will review steps (a c) and then,
- (d2) ask the participant to list the components. The clinician will provide reinforcement and cues for any strategy components the participant is unable to independently identify. The clinician will also ask the participant to describe any recent instances in which they had success using the strategy at home or out in the community.

Figure 2. Semantic Feature Analysis chart with the six strategy components

Naming Treatment Plus Strategy Application.

- (e) The clinician will place a picture of an object from the treatment list in front of the participant and ask whether the participant can name it. If the participant says no, the clinician will ask them what they should do next (circumlocute) and encourage them to do so. If the participant says yes, they will name the object and the clinician will ask the participant what they would have done *had they been unable* to name it (circumlocute) and encourage them to do so.
- (f) The clinician will encourage the participant to provide as many features as they can during circumlocution. This step engages the participant in *independent feature generation*, identified as the "active ingredient," of SFA³⁷.
- (g) The clinician will ask the participant to identify which of the strategy's components their description included (e.g., If they described a **dog** as, "an **animal** that **barks**," they would identify their description as having included the **category** and **action** strategy components). This step reinforces their knowledge of the strategy's components.

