Aim 1b. Determine whether PWA learn the strategy and consequently demonstrate a change in their language behavior in moments of naming difficulty. Analyses: We will use visual inspection to examine participants' identification of the strategy components from Treatment Week 2, to Week 8, to post-treatment sessions. We will calculate effect sizes to measure the effect of treatment on the total number of feature words produced during naming assessments and on the average number of feature words produced per naming attempt during assessments, from pre- to post-treatment. Hypotheses: We expect that strategy training will result in participants' ability to identify all six strategy components by Week 8 and at least four of the strategy components during maintenance/retention sessions. We also hypothesize that strategy training will lead PWA to produce more feature words (i.e., engage in circumlocution) during moments of naming difficulty. Specifically, we expect to find medium to large effects on the number of feature words PWA produce during naming attempts.

Aim 2. Evaluate the effect of strategy training on patients' language production during connected speech. Statistical Analyses: We will calculate effect sizes to measure the effect of treatment on number of object words, feature words, CIUs, and CIUs/minute participants produce during connected speech tasks. Hypotheses: We hypothesize that strategy training will lead PWA to produce more object and feature words during connected speech. We expect medium to large effects on object words, feature words, CIUs, and CIUs/minute during connected speech from pre- to post-treatment.

Additional analyses: We will create mixed-effects models using treatment-phase data (e.g., strategy component identification) as fixed effects, and pre-treatment cognitive-linguistic measures (e.g., CLQT+ results) and participant characteristics (e.g., aphasia severity) as random effects to further understand post-treatment outcomes. We will calculate normalized change scores to measure participants' overall improvement relative to their baseline performance and maximum possible change⁵⁶. We will report changes between participants' pre- and post-treatment WAB-R Aphasia Quotient⁴⁶ scores using the benchmarks proposed by Gilmore and colleagues³³.

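### Aim 2 and most hypotheses credit strategy training, but the design estimates only change with the combined treatment; separately, circumlocution-facilitated naming is hypothesized without a scoring rule or analysis

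*Combined protocol and SAP*

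**What the plan says.** **Attribution.** II Specific Aims gives the purpose of Aim 2 as "Evaluate the effect of strategy training on patients' language production during connected speech". Its hypothesis, in II and again in VI.c, is "We hypothesize that strategy training will lead PWA to produce more object and feature words during connected speech". The untrained-object part of the Aim 1a hypothesis and both Aim 1b hypotheses (component identification and feature words) also name strategy training as the cause. Only the trained-object hypothesis credits naming treatment.

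**Design.** IV.a states that "all participants receive the same intervention protocol", and IV.c says no assignment or randomization is needed. Under V.a Phase 2 every session contains Strategy Education, a block joining naming treatment with strategy application, and a debrief. Strategy Education step (d1) teaches "the six types of feature words they can produce during circumlocution (i.e., the six SFA framework components". Step (f) reads "The clinician will encourage the participant to provide as many features as they can during circumlocution", and the text then identifies this feature generation as the active ingredient of SFA.

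**Analysis.** The Aim 2 analysis in VI.c is "We will calculate effect sizes to measure the effect of treatment on number of object words, feature words, CIUs, and CIUs/minute". For Aim 1b it is "We will calculate effect sizes to measure the effect of treatment on the total number of feature words produced during naming assessments", plus the average per naming attempt. Aim 1a uses effect sizes for naming accuracy by object set. Under additional analyses, "We will create mixed-effects models using treatment-phase data (e.g., strategy component identification) as fixed effects".

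**Circumlocution-facilitated naming.** An increase is hypothesized for untrained objects in II and for untrained unrelated objects in VI.c. V.a, V.e and VI.a provide for collecting accuracy and pre-naming verbal attempts at the assessments.

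**The concern.** The aim and hypotheses name one quantity and the analysis estimates another. I.c presents SFA and strategy training as two components with different purposes, and the Aim 1a hypothesis assigns trained-object gains to one and untrained-object gains to the other. A reader could therefore take a positive Aim 2 result as evidence for the strategy component, which this design cannot isolate. The expected-results sentence in I.c invites the same reading.

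The second issue concerns Aim 1a. One half of the untrained-object hypothesis is about how the name was reached. The planned analysis looks only at whether it was reached. Aim 1b counts feature words but does not tie them to whether the object was then named. That half of the hypothesis has no planned answer, although the raw material for one is to be collected.

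**Working it through.** The plan gives no figure of its own on this point. The check sets the text side by side and then uses small arithmetic.

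**1. Cause named against analysis planned (VI.c).**

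| Hypothesized result | Cause named | Planned analysis |
|---|---|---|
| Trained-object naming | naming treatment | effect size, treatment |
| Circumlocution-facilitated naming, untrained | strategy training | none specific |
| Untrained-object accuracy | strategy training | effect size, treatment |
| Component identification | strategy training | visual inspection |
| Feature words in naming attempts | strategy training | effect size, treatment |
| Object and feature words in connected speech | strategy training | effect size, treatment |
| CIUs and CIUs/minute | none named, under Aim 2 | effect size, treatment |

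Five of seven name strategy training. All three effect-size sentences (Aims 1a, 1b and 2) refer to treatment.

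**2. Can the components be separated?** Write outcome = a + b × SFA + c × strategy. Both indicators are 0 at the 3 baselines and 1 in all 3 × 8 = 24 treatment sessions. The columns are identical, so the model reduces to a + (b + c) × treatment. The design matrix has rank 2 for 3 columns. Only b + c is estimable, whatever the number of participants.

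**3. Repeated testing (secondary).** Each object is shown at 3 baselines. Weekly probes number 7 (Weeks 2 to 8, V.a) or 8 (V.e). The stopping rule of three consecutive probes over 90% could end treatment after 3. A weekly-probed object may thus be shown 3 + 3 = 6 to 3 + 8 = 11 times before post-treatment assessment, assuming the full probe list is shown each time. The count does not apply to never-probed objects or to connected speech.

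**4. Naming route (illustration only).** The documents give no set sizes. Eligibility of 1 to 146 correct of 176 means 176 − 146 = 30 to 176 − 1 = 175 objects missed at the first assessment. An assumed equal three-way split gives 10 to about 58 untrained objects, so I use 10 and 60. Entries are named directly / named after a feature word / not named.

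| Set | Pre | Post, route A | Post, route B |
|---|---|---|---|
| 60 | 10/5/45 | 20/5/35 | 10/15/35 |
| 10 | 2/1/7 | 4/1/5 | 2/3/5 |

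The effect size in VI.c is (post mean − pre mean) / pre SD.

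- If a name after a feature word scores as correct, accuracy in the 60-object set goes from 15 to 25 on both routes, so the effect size is the same whatever the SD. Naming after a feature word stays at 5/60 = 8.3% in A and reaches 15/60 = 25.0% in B. In the 10-object set accuracy goes from 3 to 5 on both routes, against shares of 1/10 = 10% and 3/10 = 30%.
- If only direct names score, accuracy in the 60-object set goes from 10 to 20 in A and from 10 to 10 in B. The routes then differ, but the facilitated names drop out of the measure.

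**5. Selection of objects.** V.a Phase 1 puts an object on the list if it is missed on at least one of three baselines. With no treatment effect, independent responses and true accuracy p, the expected baseline accuracy of a listed object is (p − p³)/(1 − p³).

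- p = 0.5: 0.375/0.875 = 0.43, against 0.50 afterwards.
- p = 0.7: 0.357/0.657 = 0.54, against 0.70 afterwards.

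Some rise is therefore expected from regression to the mean alone.

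**The case against.** The single-protocol design is openly stated. The study title and Aim 1 already speak of naming treatment that incorporates strategy training, and the analyses are already worded as effects of treatment. On that view this is loose wording, and only Aim 2's own statement of purpose is wrong. That stands as a limit on severity. It does not remove the mismatch, because the hypotheses assign different gains to different components.

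The plan also offers partial support for attribution. Three baselines and visual inspection help to judge drift in the combined effect, but they do not say which component caused a change and are not a concurrent control. Untrained unrelated objects, set against the statement in I.b that most restorative treatments do not generalize to them, give an informal historical contrast. For connected speech I.b calls the evidence inconsistent, so Aim 2 has no such benchmark. The mixed model relates component knowledge to outcome within one cohort, which is an association. Component identification is a fair exception: it is taught directly, so attribution is more plausible there.

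On facilitated naming, V.a says pre-naming verbalizations will be transcribed for later characterization, and VI.c applies its methods to all results. Aim 1b feature-word counts would tend to differ between the two routes. V.e also collects accuracy before and after feature generation. None of this supplies a rule linking a feature word to a later name, and the before-and-after accuracy covers treatment objects in clinician-led sessions only.

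**Conclusion.** Both parts hold, and the plan should be changed. In the first, Aim 2 and four of the seven hypothesized results (the five credited to strategy training, less component identification) claim more than pre-post change with the combined treatment. This follows from the design and needs no numerical assumption. In the second, one stated hypothesis has no planned answer. The loss of information in the accuracy effect size depends on a name after a feature word being scored as correct, which the plan leaves open.

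A reader might infer stronger conclusions that the documents do not support:

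- That the planned estimates are invalid or that a comparison arm is required. The effect sizes remain valid descriptions of change; only the conclusion narrows.
- That repeated testing explains the results. The count of 6 to 11 showings concerns weekly-probed objects only and does not bear on separating the components.
- That accuracy can never distinguish the naming routes. With direct-only scoring it can.
- That data for the facilitated-naming question are missing. They are to be collected; the rule and the analysis are what is absent.

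The 10- and 60-object counts are assumed and say nothing about what this trial will find.

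**What to change.** **Attribution.** Restate Aim 2, the untrained-object part of the Aim 1a hypothesis, the Aim 1b feature-word hypothesis and the Aim 2 hypothesis as change with the combined SFA-plus-strategy treatment. Add three statements: the separate contribution of strategy training is not estimated; repeated-testing and time effects are not excluded; the mixed-model result for component identification is a within-cohort association. Keep component identification as a check that the taught content was learned over the combined treatment. Narrow the expected-results sentence in I.c in the same way.

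**Facilitated naming.** Before coding, write a rule that classes each response as named directly, named correctly after at least one feature word, or not named. Say whether the second class counts in Aim 1a accuracy. Report pre and post counts for untrained objects, with related, unrelated and weekly-probed objects shown separately. Name the assessments that enter the pre and post figures: V.e mentions six post-treatment sessions and VI.c does not say which are averaged. State that listed objects were selected for a baseline miss, so some rise is expected without any effect. Describe the result as naming route, not as proof of facilitation.

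**Cost.** Wording changes, one scoring rule, some extra transcript coding and a narrower claim. Cells will be small where object sets are small. IV.b lets participants decline recording, so report how many lack the recordings needed.
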